If subjects participate at WIC, the research will be conducted at the same time and place where subjects regularly obtain their WIC voucher so as to be convenient for the subjects.

Participants always have the choice NOT to answer questions if they choose not to or have the ability to withdraw from the study at any time without penalty.

As noted in our consent form, if the participant “indicates that your child is in danger of being seriously harmed, or you or your child are in danger of hurting someone, the research staff is required by law to report this information to the appropriate agency personnel.” We have established a clear child abuse reporting protocol for our staff. This protocol has been developed and reviewed in collaboration with [name], Director of CBNO.

Minimizing Risks and Monitoring Data: The investigators will ensure that proscribed confidentiality measures are followed and will provide extensive training to all staff to ensure that protocols are being followed. As part of their employment contract, all staff will be asked to sign a form stating that they will not breach any of the confidentiality protocols. All information will be coded with a subject identification number. Any identifying information collected will remain separate from study database and hard copies will be stored in locked cabinets in the PI's secure office and will be destroyed following study conclusion. Only aggregated data will be reported in the study results; no names or other identifying information will be reported.

Subject code numbers for each child will be assigned at the time of consent and will be based on their mother's ID number and will not include any other information.

Materials generated under the project will be disseminated in accordance with University and funder policies. Publication of data shall occur during the project, if appropriate, or at the end of the project, consistent with normal scientific practices. Research data which documents, supports and validates research findings will be made available after the main findings from the final research data set have been accepted for publication. Such research data will be redacted to prevent the disclosure of personal identifiers.

Computers that will be utilized during all phases of this proposal are password and software encrypted to prevent inappropriate access to information. All data will be stored in electronic format using password protection and encryption on the database. All unique identifiers will be protected as described above.

6. Benefits

There will be no direct benefits to subjects for participating in this research, but the knowledge gained from the study may benefit society in general. Anticipated benefits might include a participant's greater understanding of positive parenting techniques.

7. Remuneration

At the Baseline visit, a Team Member will pay the participant with a \$25 gift card to a local retailer as recommended by our WIC partners before the participant leaves the site. Then, at the 3-month follow-up visit to the study site, once the follow-up interview is completed, a Team Member will pay the participant with another \$25 gift card, for a total of \$50 in gift cards. If the participant completes the 1-year follow interview, a Team Member will provide the participant with comparable remuneration to the first two interviews.

Upon completion of the Long Term follow-up visit, a participant will receive a \$50 gift card for completion of the Long Term follow-up survey if completed by phone, and a \$75 gift card for completion

of the in-clinic observational activities - if and when they are completed at a later date. Alternatively, if the participant completes both components of the visit at the same time in the clinic, they will receive a \$125 gift card.

8. Academic or Extra Credit

N/A

9. Costs

There will be no costs to the subject for participating in this research study.

10. Alternatives

Subjects always have the option to not participate in the research.

11. Consent process and documentation

The informed consent process will include providing a copy of the consent form to the parent, reviewing the content of the consent form with the parent, answering any questions she might have, and, if she agrees to participate, having her initial each page and sign and date the final page of the consent form. On the long term follow-up consent form, the participant will also initial as to whether or not they consent to being recorded and whether or not they consent to have video recordings stored for future studies after the close of the study, all of which will be tracked in the REDCap database and used to guide data collection, video storage procedures and data cleaning and analysis. Our staff will also sign and date the final page. Once the parent has finished reading each page, the Team Member will review the content of the consent form and highlight particularly important points, namely: (1) their decision to participate is completely voluntary in nature and (2) does not affect their receipt of WIC services, (3) they will be randomly assigned to one of three groups, (4) they may withdraw or refuse to answer any questions at any time, and (5) their personal information will be kept confidential.

The Team Member conducting the interview will remind the participant that all responses are optional, that she can choose to end her participation at any point and will ask the participant if she has any questions. This reminder will be reiterated before all follow-up surveys and throughout the course of all interviews.

The reminder call made one week before the second scheduled meeting will be made using a script to prevent unintentional coercion.

If a Follow-Up Survey is conducted via telephone, the team member will read the Oral Consent Script, receive oral consent from participant for additional interviews, and the team member will provide written documentation of consent.

Because the compensation is a maximum of \$75 per visit or study section, there is little possibility of coercion or undue influence.

References

1. Children's Bureau. *Child Maltreatment 2011*.: U.S. Department of Health & Human Services, Administration for Children and Families, Administration on Children Youth and Families;2012.

Cover Page

Statistical Analysis Plan

Study Title: Longitudinal Follow-up of Brief Parenting Interventions to Reduce Risk of Child Physical Maltreatment

Identifier: NCT04059185

Document date: 04/18/2024

Statistical Analysis Plan

The power analysis was based on the continuous primary outcome scores at 3-month follow-up. Assuming a significance level of 0.05 in two-tailed tests for the interaction between treatment group and visit type (baseline and follow-up), we would have at least 90% power to detect a standardized effect size of 0.33, if we enrolled 300 participants per group. Conservatively we allowed for a modest amount of autocorrelation of 0.30.

The reported results will follow an Intent to Treat analysis. For the baseline to 3 month follow up analysis, we will fit linear mixed effect models for each of the scale outcomes: Attitudes towards Spanking Scale (ATS), Positive Parenting Practices scale (PPP) and Child Emotional Maladjustment (CEM). The predictors in the models will be group membership (TP2, PN, and Control), visit type (baseline and follow-up) and their interaction along with random intercepts for subjects. We will also report contrasts among treatment groups and visit type based on post-hoc least squares means analyses, using a Benjamini and Hochberg correction to adjust for false discovery rate for multiple comparisons. As a robustness check, we will use difference scores as the outcomes in linear regression model. We will use Full Information Maximum Likelihood to address missingness. Generalized Estimating Equations with a multinomial outcome will be used for the categorical outcome. We will use multiple imputation to maximize use of all available data.

For the 4 year follow up (4Y) analysis, we will fit linear mixed effect models for each of the scale outcomes: ATS, PPP (total and 4 subscales) and CEM (total and 2 subscales). The predictors in the models will be group membership (TP2, PN, and Control), visit type (baseline, 3M, 4Y), and their interaction. Models will also include random intercepts for participants. Generalized estimating equations (GEE's) will be used for the nominal multinomial outcome of spanking behavior, accounting for within-person correlation across timepoints.

Multiple imputation using chained equations will be used to address missingness and unusually delayed 4Y visits due to the COVID-19 pandemic (number of imputations = 100). Specifically, a new column will be created for “4-year-follow-up” responses on all primary outcomes and filled in with the participant’s true response if they were visited within 5.1 years of their baseline visit (i.e. if their follow-up time was below the third quartile for the sample follow-up time); Otherwise, this value will be set as “missing” and therefore imputed using the multiple imputation procedure. The imputation model will include participants’ actual long-term response values and their observed time lag to long-term visit from baseline interview date, in addition to the primary measures used in the study at all time points, demographic information, and intervention group.

For the RSA outcome measures, linear mixed effects models will be employed to model the effect of the intervention condition on task specific RSA withdrawals. For these questions, children and parent data will be analyzed separately, and the specified model will be identical for both populations. The model will include mean RSA as the dependent variable. Predictors will include Epoch (baseline, social interaction task, or challenge task), Intervention Group, and the interaction of these terms. Random intercepts for participant ID will account for repeated measures across epochs.

After fitting the model, hypotheses will be tested with a series of planned contrasts. Specifically, we will evaluate the statistical significance of the following contrasts:

- TP vs. Control at Baseline, Social Interaction, and Challenge (Hypothesis a; 3 tests)
- PN vs. Control at Baseline, Social Interaction, and Challenge (Hypothesis b; 3 tests)
- Effect of Social Interaction epoch with reference to Baseline for TP vs Control (Hypothesis c, 1 test)
- Effect of Social interaction epoch with reference to Baseline for PN vs. Control (Hypothesis d, 1 test)

- Effect of Challenge task epoch with reference to Baseline for TP vs Control (Hypothesis e, 1 test)
- Effect of Challenge task epoch with reference to Baseline for PN vs. Control (Hypothesis f, 1 test)

As a robustness check, we will also fit alternative models to test Hypotheses c and d. These will be linear regression models in which the outcome represents RSA withdrawal from baseline (Baseline RSA – Social Interaction RSA), and the predictor is Intervention Group. This model will not include Epoch or any random effects.

To address research questions related to the CIB, we will compare the three treatment groups along all sub-constructs of the CIB, with primary focus on comparing each intervention group to the control group. The CIB sub-constructs include three maternal outcomes (maternal intrusiveness, maternal sensitivity, and limit setting), three child outcomes (engagement, compliance, and withdrawal), and two dyad-level outcomes (dyadic reciprocity and negative states). We specifically hypothesize that maternal intrusiveness, child withdrawal, and dyadic negative states will be lower in both intervention groups compared to the control group, and that maternal sensitivity and limit setting, child involvement and compliance, and dyadic reciprocity will be higher in both intervention groups compared to control. We will fit linear mixed effects models for each outcome. The predictors in the models will include fixed effects for Epoch (social interaction task or challenge task), Intervention Group (reference=control group), and the interaction of these terms. Random intercepts for participant ID will account for repeated measures across epochs. Because we have no specific hypothesis that the intervention effect will vary across tasks, we will drop the interaction term if it is not significant based on a likelihood ratio test (LRT). In this case, we would interpret the main effects of each intervention group indicator using a LRT to test the study hypotheses.

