WIC clients may also learn about the study before they arrive at WIC for their regularly scheduled appointments (i.e. before we would typically recruit them, per the above). WIC has offered and kindly agreed to mail a TIPPS recruitment flyer to WIC Clients' homes along with WIC's appointment reminder packets. This new "mailer flyer" presents basic study information and informs interested individuals how to contact our TIPPS staff. At the time they call, a TIPPS Research Coordinator will confirm the individual's eligibility and request that she alert WIC staff of her intention to enroll in TIPPS when she arrives for her WIC appointment.

For open recruitment, anyone that learns about the study via another source will contact TIPPS and schedule an appointment at a study site.

Consent and Enrollment: A TIPPS Team Member will then take the parent through the informed consent process utilizing the Updated Informed Consent – New Participant form. This will include providing a copy of the consent form to the parent, reviewing the content of the consent form with the parent, answering any questions she might have, and, if she agrees to participate, having her initial each page and sign and date the final page. Our staff will also sign and date the final page. Our staff will then administer a comprehensive Contact Information Form. Once this is complete, our staff will assign a participant ID and perform random group assignment. The Team Member conducting the baseline interview will remain blinded to the group assignment until the interview is complete.

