copy of the consent form to the participant, reviewing the content of the consent form with the parent, answering any questions she might have, and, if she agrees to participate, having her initial each page and sign and date the final page. Our staff will also sign and date the final page. For telephone interviews, this will include reviewing the oral consent script before beginning the interview, answering any questions she might have, and, recording written documentation if she agrees to participate. The Updated Baseline Consent Form ensures all participants are presented with the opportunity to participate in future TIPPS interviews, as well as be contacted to participate in future research. Parents that express interest in additional parenting advice or services will be given a Resource Guide and, if needed, provided with a referral to the Children's Bureau for additional help and guidance.

It is common for as many as 50% of WIC participants to miss their scheduled WIC visits. If a participant misses her 3-month follow-up visit for our study, our team will contact the participant and try to reschedule the visit. We will continue trying to reschedule and complete this visit for up to 6 months. If the participant has moved or is otherwise unable to return to WIC, but is willing to complete the interview via phone, we will do so. After 6 months post baseline, if no follow-up data is obtained, we will code the participant as "lost to follow-up."

Despite our best efforts to retain all of our study participants, we anticipate a 75% retention rate. In other words, we expect that at least 25% of our baseline sample (n=1200) will not return to provide follow-up data. Hence, we expect our final 3-month sample to include 900 participants.

Data Security: Data will be stored on Tulane's secure REDCAP server. Only the PI, Cols, and the Program Manager will be able to download the data onto their own computers for data analysis. All computers are password protected.

Due to grant funding limits, not all participants may be able to participate in a 1-Year Follow Up. The protocol below is for those participants who are scheduled to complete their 1-Year Follow-Up before grant funding for TIPPS is complete.

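### The mixed models for the scale outcomes leave baseline as a free outcome in each arm; at the SAP's correlation of 0.30 the powered 3-month test carries about 40% more variance than a baseline-adjusted comparison

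*SAP*

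**What the plan says.** The SAP's 3-month paragraph models each scale outcome (ATS, PPP, CEM) with "group membership (TP2, PN, and Control), visit type (baseline and follow-up) and their interaction along with random intercepts for subjects". The opening power paragraph names the group-by-visit interaction as the powered test and states that "we allowed for a modest amount of autocorrelation of 0.30", a value it calls conservative. For missing data it says "We will use Full Information Maximum Likelihood to address missingness". It adds: "We will also report contrasts among treatment groups and visit type based on post-hoc least squares means analyses". As a robustness check, "we will use difference scores as the outcomes in linear regression model".

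The 4-year paragraph uses the same structure, with group membership, "visit type (baseline, 3M, 4Y), and their interaction". No baseline covariate and no common-baseline constraint is stated for any scale-outcome model.

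Three parts of Protocol section 3 (Procedure) bear on this:

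- Consent and Enrollment places random assignment before the baseline interview, but says: "The Team Member conducting the baseline interview will remain blinded to the group assignment until the interview is complete".
- Baseline Interview has the participant told her group only once that interview is over; the intervention follows.
- The 3-month follow-up text says "we anticipate a 75% retention rate", taking 1200 enrolled to 900 followed.

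**The concern.** With a free baseline mean in every arm, the interaction subtracts each arm's observed baseline mean from its follow-up mean. Randomisation makes the true baseline means equal, so the subtraction mostly adds the sampling noise of the baseline means. Assignment here comes before the baseline interview, so the equality cannot be justified by timing. It is justified by concealment, because neither the interviewer nor the participant knows the group while the baseline answers are given. On that footing, a model with a common baseline mean, or with baseline as a covariate, targets the same effect with smaller variance.

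What is at stake is precision for effects below the planning value of 0.33 SD. Those effects matter to this trial: the Study Design section of the Protocol argues that even a small risk reduction is worthwhile when spread over a large population.

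The one robustness check does not probe the choice either. A difference-score regression on group estimates the same change contrast. In complete pairs it equals the mixed-model interaction, and otherwise it differs only in which participants are included.

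**Working it through.** **Inputs.** Two-sided alpha 0.05, effect 0.33 SD, 300 per group and correlation ρ = 0.30 (SAP power paragraph). 1200 enrolled (Protocol section 2) and 75% retention (Protocol section 3). Assumed: equal allocation, giving n₀ = 400 at baseline and n₁ = 300 at 3 months per arm; equal SDs at both visits; loss completely at random.

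**The plan's own figure.** With 300 complete pairs per arm, the SE of the difference in change is √(2 × 2(1 − 0.30)/300) = √(2.8/300) = 0.0966. Then 0.33/0.0966 = 3.416, and power is Φ(3.416 − 1.96) = 92.7%. This meets the stated floor of 90%.

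**Variance per arm, unit SD.**

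- Interaction under FIML: (1 − ρ²)/n₁ + (1 − ρ)²/n₀
- Follow-up least-squares mean, free baselines: (1 − ρ²)/n₁ + ρ²/n₀
- Equal-baseline or baseline-adjusted: (1 − ρ²)/n₁
- Difference scores, complete pairs: 2(1 − ρ)/n₁

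**At ρ = 0.30.** The interaction gives 0.91/300 + 0.49/400 = 0.004258. Adjusted gives 0.91/300 = 0.003033. The ratio is 1.404. The table shows per-arm variance × 300.

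| Comparison | Variance × 300 | SE of arm contrast | Excess over adjusted | Power, 0.25 SD |
|---|---|---|---|---|
| Interaction, FIML (planned) | 1.2775 | 0.0923 | 40% | 77% |
| Follow-up LS means | 0.9775 | 0.0807 | 7% | 87% |
| Baseline-adjusted | 0.91 | 0.0779 | – | 89% |
| Difference score | 1.40 | 0.0966 | 54% | 74% |

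- Effect detectable with 90% power, (1.96 + 1.2816) × SE: 0.299 SD planned, 0.252 SD adjusted.
- Power for 0.20 SD: 58% planned, 73% adjusted.
- Power for 0.33 SD: 94.7% planned, 98.9% adjusted.
- Followed participants per arm at which adjustment matches the planned test: 300 × 0.91/1.2775 ≈ 214.

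**Dependence on ρ.** With two visits and a fraction f followed, the interaction's excess is f(1 − ρ)²/(1 − ρ²) = f(1 − ρ)/(1 + ρ), positive for every ρ below 1. The follow-up contrast's excess is fρ²/(1 − ρ²). At f = 0.75:

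| ρ | Interaction excess | Follow-up LS means excess | Power for 0.25 SD, interaction vs adjusted |
|---|---|---|---|
| 0.3 | 40% | 7% | 77% vs 89% |
| 0.5 | 25% | 25% | 88% vs 94% |
| 0.7 | 13% | 72% | 98% vs 99% |

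**Numerical checks.** The exact three-arm generalised-least-squares information matrix gives contrast variances of 0.008517 and 0.006067, ratio 1.404. In 20,000 simulated trials with 25% random loss and a true effect of 0.25 SD, all four estimators averaged 0.250. Their empirical SEs were 0.0928 (interaction), 0.0805 (follow-up contrast), 0.0779 (adjusted) and 0.0969 (difference score). The interaction and difference-score estimates correlated 0.96.

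**The case against.** The planned model is standard and valid, and its stated power is met. The strongest points in its favour are these.

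- **0.30 is a cautious planning value.** If the true correlation is 0.7, little power is lost. This stands as a limit on the size. The sign does not change at any correlation below 1.
- **A near-efficient contrast may already be planned.** The least-squares-means contrasts can include arm comparisons at follow-up, with only 7% excess at ρ = 0.30. But the SAP labels them post hoc and powers the interaction, and the follow-up contrast's excess grows with ρ while the interaction's shrinks. Adjustment is at least as good as both, without having to guess ρ.
- **The difference-score regression lists no predictors.** If baseline were among them, its group coefficient would be identical to that from regressing follow-up on baseline. However, the SAP's parallel RSA check, also on a change from baseline, names group as its only predictor, so a group-only regression is the natural reading.
- **The SAP is late.** It is dated 04/18/2024 and uses a sample quartile of long-term follow-up time, so 3-month data were probably collected well before. Whether arm-level results had been seen is not stated. This stands and shapes the fix.
- **The equal-baseline assumption needs the blinding to have held.** This also stands. The Protocol describes the blinding but does not detail how the allocation was concealed.
- **The power figures are for one pairwise test at 0.05.** They ignore the Benjamini-Hochberg step. A 2-df interaction test at 0.33 SD with 300 complete pairs per arm has 87% to 95% power, depending on the third arm's mean. The variance ratio for the pairwise contrasts is unaffected.

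**Conclusion.** The concern holds as a loss of efficiency, not as bias. For the powered 3-month test the excess variance is 40% at the SAP's own correlation, falling to 25% at 0.5 and 13% at 0.7. The practical effect is on differences of about 0.20 to 0.25 SD; at 0.33 SD power is already high.

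The result rests on the assumptions listed with the inputs and on a blinded baseline interview. The variance ratio depends only on the correlation and the retention fraction, so it is unaffected by the SAP counting 300 per group as enrolled while the Protocol's figures make 300 the number followed. Power does depend on that: with 300 enrolled and 225 followed per arm, power for 0.33 SD would be about 87% planned and 96% adjusted.

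The 4-year model shares the structure, but its loss is not quantified. The documents give no 4-year correlation, and that analysis has three visits, 100 imputations and late visits reset to missing.

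**What to change.** In the 3-month and 4-year mixed models, constrain the three baseline means to be equal: omit the group main effect and keep the group-by-follow-up-visit terms. Cite the blinded baseline interview as the reason. Using baseline as a covariate is an acceptable alternative. Name TP2 versus control and PN versus control, at 3 months and at 4 years, as the tests. Replace the difference-score check with a regression of follow-up on baseline and group.

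If anyone responsible for the analysis has already seen results by arm, keep the planned model as primary and add the baseline-adjusted model as the robustness check. The SAP should state which situation applies.

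The change is to SAP wording only, since the baseline interview already precedes the intervention for every participant. There are two small costs: the effect is reported as a baseline-adjusted follow-up difference rather than a difference in change, and the constraint depends on the baseline interview having stayed blinded.

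### The 4-year scale models rest on a random intercept alone across three unevenly spaced visits, and the SAP's difference-score check is not carried to 4 years

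*SAP*

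**What the plan says.** The 4-year paragraph of the SAP specifies linear mixed models for ATS, PPP and CEM with group, "visit type (baseline, 3M, 4Y), and their interaction. Models will also include random intercepts for participants". It names no residual covariance structure and no robust standard error for these models.

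The preceding paragraph, on the baseline-to-3-month analysis, adds a safeguard: "As a robustness check, we will use difference scores as the outcomes in linear regression model". The 4-year paragraph and the imputation text that follows it have no counterpart.

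The power paragraph frames the test as "two-tailed tests for the interaction between treatment group and visit type", for baseline and 3 months. It supplies the only correlation in the documents: "Conservatively we allowed for a modest amount of autocorrelation of 0.30". The 4-year paragraph does not say whether its test is the baseline-to-4-year change or the group difference at 4 years.

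The RSA model has the same form over three epochs: "Random intercepts for participant ID will account for repeated measures across epochs". There the SAP does add a change-score check, but only for two of the four change hypotheses: "As a robustness check, we will also fit alternative models to test Hypotheses c and d". Hypotheses e and f, on the challenge task, have none.

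**The concern.** With two visits and complete data, a random-intercept interaction test and a difference-score regression essentially coincide, so the 3-month analysis is safe. With three visits they can differ. The model estimates one within-person variance, pooled over all three pairs of visits, and uses it for every change contrast.

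The visits are far from evenly spaced. The first follow-up is at about 3 months. Under the protocol's Long Term Follow-Up procedure, scheduling starts no earlier than 23 months after baseline, and the SAP puts the third quartile of follow-up time at 5.1 years. Scores 3 months apart may well correlate more strongly than scores 4 years apart. If so, and if SDs are similar, the pooled variance is too small for the baseline-to-4-year change. Its standard error is then too small and its test rejects too often.

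If SDs change between visits as children age, the 4-year group difference is affected too, in either direction. Sustained effect is a stated protocol aim, so these are the standard errors behind the long-term claim, and no planned check would reveal a problem.

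**Working it through.** **The SAP's own figure.** Inputs from the power paragraph: 300 per group, effect 0.33 SD, correlation 0.30, two-sided 5%. The SD of change is √(2 × (1 − 0.30)) = 1.183. The SE of the group contrast is 1.183 × √(2/300) = 0.0966. The ratio 0.33/0.0966 is 3.416, and power is Φ(3.416 − 1.96) = 92.7%. The stated figure of at least 90% is reproduced. It concerns 3 months only and is not in question.

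**Formula for 4 years.** With saturated group-by-visit means and complete data, the random-intercept fit uses the mean variance v and the mean covariance c over the three visits.
- Model variance of the baseline-to-4-year change is proportional to 2(v − c).
- True variance is proportional to var(BL) + var(4Y) − 2cov(BL,4Y).
- SE ratio = √(model/true), and actual type I error = 2Φ(−1.96 × SE ratio).

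**Change contrast.** SDs are equal. All correlations are assumed, except that 0.30 for baseline-3M in the first row is the SAP's value. Order: baseline-3M / baseline-4Y / 3M-4Y.

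| Correlations | Model variance | True variance | SE ratio | Type I error |
|---|---|---|---|---|
| 0.30/0.20/0.20 | 1.533 | 1.600 | 0.98 | 5.5% |
| 0.5/0.3/0.3 | 1.267 | 1.400 | 0.95 | 6.2% |
| 0.7/0.3/0.4 | 1.067 | 1.400 | 0.87 | 8.7% |
| 0.5/0.4/0.3 | 1.200 | 1.200 | 1.00 | 5.0% |
| 0.3/0.3/0.3 | 1.400 | 1.400 | 1.00 | 5.0% |

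Direct REML fits (3 groups of 300, 8 datasets each) agree for the first three rows: SE 0.1017 against 0.1039 under an unrestricted covariance (0.98), 0.0919 against 0.0970 (0.95), and 0.0835 against 0.0955 (0.87).

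**Imputation.** The SAP keeps an observed 4-year value only "if their follow-up time was below the third quartile for the sample follow-up time", so about 25% of observed values are set to missing. For a share f imputed completely at random, f/(1 − f) times the residual variance of the 4-year score given baseline and 3 months is added to both variances. In the first row the residual variance is 0.9385. At f = 0.25 the ratio is √((1.533 + 0.313)/(1.600 + 0.313)) = 0.982, giving 5.4%.
- f = 0.25: the first three rows become 5.4%, 6.0% and 7.9%. This overstates the dilution from the late-visit rule alone, because the late responses are themselves predictors in the imputation model.
- f = 0.44: 5.3%, 5.8% and 7.3%. This is 1 − 0.75 × 0.75, and assumes the protocol's 3-month expectation ("we anticipate a 75% retention rate") also held at 4 years.

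A simulation with 40% imputed (two arms of 300, 30 imputations, 3000 runs, Monte Carlo SE about 0.4 points) gave 6.1%, 5.8% and 7.4% for the random intercept, against 5.8%, 5.1% and 5.1% for an unrestricted covariance. Only the third scenario is clearly separated from noise.

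**Group difference at 4 years.** The model uses v; the truth is var(4Y).
- Equal SDs: 5.0%.
- 4-year SD 1.2 times the others: v = (1 + 1 + 1.44)/3 = 1.147, ratio √(1.147/1.44) = 0.89, error 8.0% (6.6% with 44% imputed, at correlations 0.30/0.20/0.20).
- 4-year SD 0.8 times the others: v = 0.88, ratio √(0.88/0.64) = 1.17, error 2.2% (3.1% with 44% imputed, same correlations).

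A smaller 4-year SD can also cancel the shortfall in the change contrast. At 0.5/0.4/0.4 with SD 0.8, v = 0.88 and c = (0.50 + 0.32 + 0.32)/3 = 0.38, so the model variance is 1.00. The true variance is 1 + 0.64 − 0.64 = 1.00, so the ratio is 1.00.

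**RSA hypotheses e and f.** Equal SDs; assumed correlations in the order baseline-social / baseline-challenge / social-challenge. 0.8/0.7/0.75 gives √(0.25/0.30) = 0.91 and 7.4%. 0.7/0.7/0.7 gives 5.0%. 0.7/0.8/0.7 gives √(0.267/0.20) = 1.15 and 2.4%.

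**The case against.** The strongest reply is that no error is demonstrated. Apart from 0.30, every correlation and SD above is assumed, and if 0.30 held for all pairs with equal SDs the test would be exact. The larger figures need strong inputs. With both 4-year correlations at 0.3 and equal SDs, error above 7% needs a baseline-3M correlation above about 0.61 with complete data, or about 0.76 with 44% imputed. With baseline-3M at 0.30 and both 4-year correlations at zero, error is 6.3% (5.9% with 44% imputed). All of this stands, and it is why the size is put no higher than minor to moderate.

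It is also fair that the SAP does not exclude another residual structure. The reading here is the usual default when nothing is said; if something else was intended, one sentence settles it. If the 4-year test is the group difference and SDs are equal across visits, the correlation problem disappears. The SAP does not commit to that contrast, and the documents give no SDs by visit.

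Multiple imputation does not answer the point. The within-imputation variance comes from the same model, so imputation dilutes the error without removing it. A direct likelihood fit to incomplete data would give larger errors (8.3% at 0.6/0.3/0.35 with 75% seen at 3 months and an assumed 50% at 4 years). The SAP specifies imputation, so that figure is not relied on here.

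**Conclusion.** The concern holds. As written, the three-visit scale models assume equal variances and one correlation across very unequal gaps. Nothing in the documents supports that assumption, and no 4-year check would expose its failure. The direction is not known in advance. If SDs are similar and the baseline-4Y correlation is below the mean of the three, the standard error of the 4-year change is too small. Across the assumed scenarios the actual error of a nominal 5% test is 5.0% to 8.7% with complete data; the inflated cases fall to 5.3% to 7.3% with 44% imputed. For the 4-year group difference the error is 5.0% with equal SDs, and 8.0% or 2.2% if the 4-year SD is 1.2 or 0.8 times the others. RSA hypotheses e and f carry the same uncertainty in either direction. The separate two-visit 3-month analysis and its power statement are unaffected. This should be changed because the remedy is nearly free, not because a large bias is established.

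**What to change.** - **4-year scale models:** replace the random intercept with an unstructured covariance over baseline, 3M and 4Y, fitted by REML and combined over the 100 imputations. Name robust standard errors as the fallback if it does not converge. Small-sample degrees-of-freedom corrections (Kenward-Roger or Satterthwaite) can be named but matter little with hundreds per arm.
- **Robustness check:** extend the difference-score regression to 4Y minus baseline.
- **RSA:** use an unstructured covariance over the three epochs, or extend the change-score check to hypotheses e and f.

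The cost is one or two SAP sentences and a software option. There are six covariance parameters instead of two, which several hundred participants support easily. The method stays valid if the correlations and variances are in fact equal. On the imputed, balanced data the point estimates do not change, only the standard errors. P-values for the 4-year change may become slightly less favourable, or slightly more so if the 4-year SD is smaller.
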